9.6 DATA MANAGEMENT

PHEOR's data facility is in a secured building with a security guard presence twenty-four hours a day. The facility is monitored internally and externally with video and motion-based sensors with controlled access via keycard and keypad. Computing hardware is stored on racks in locked cabinets. Remote access is either via secure IP connection, with firewalls in PHEOR offices as well as the data center, or via software VPN. Servers run Linux and use standard file permissions and auditing systems to control and monitor access to restricted data files and directories. Staff workstations will use a password-protected screen-saver, set to activate automatically after 5 minutes of non-use; the screen saver will be automatically set whenever the computer is unattended for an extended period of time. All staff workstations have standard virus software installed and maintained with regular updates and patches.

Project staff will be the only researchers granted regular access rights to the data. The only other individuals with access are PHEOR's system administrators. These individuals are PHE employees and long-term contractors who have broad responsibilities across all of the company. One copy of each original database will be made as a backup and stored in a locked safe, in a locked office at PHEOR headquarters. Derived data and programs will be backed up to a second drive system located within the same secure data facility described above; this backup process can be turned off upon request.

Original data and backups will be destroyed on or before the date on which our authorized access to the restricted data ends or at the request of any vendors. There will never be any paper printouts of the data. Any electronic listing or log files will be treated as derived data as above.

9.7 DATA ANALYSIS

9.7.1 Main analysis

As described above starting with the initiation of treatment, we observe patient outcomes until one of:

- discontinuation or switch or addition of a drug in the comparator and/or other antihyperglycemic agents class
- occurrence(s) of an outcome of interest
- nursing home admission

- healthcare plan disenrollment
- exposure to other diabetes medications
- end of the study period

Step 1: Create the matched sample

There are many variants of propensity score matching. In the simplest version, individuals in the case group are matched 1:1 with individuals in the set of candidate controls, on the basis of similarity (minimized difference) of the propensity score, using a list-wise matching process (a list-wise matching process is one in which first a match for empagliflozin add-on patient 1 is found, then a match for case member 2, iterating to finding a match case group member N at the end of the matching procedure). In K-nearest neighbors matching, case group members are matched to the K members of the candidate set of controls (where K is a small positive number such as 2, 3 or 4), again based on minimized difference in propensity score. This method can be used if the initial data inspection determines that a larger sample size is required. It can improve the precision of estimates, but may result in additional bias due to poorer matches on average. In caliper matching (which may be applied to either nearest neighbor or K-nearest neighbor variants), individuals are selected for inclusion if their propensity score distance from the matching candidate is less than some caliper parameter, c (for estimating means or risk differences, often caliper width equaling 0.2 of the standard deviation of the logit of propensity score is used for estimating risk differences or differences in means). If no acceptable match is found within the caliper, the case is dropped. Caliper matching may be required if it is necessary to ensure that all matches meet some minimally acceptable threshold for match quality; however, it may further reduce the generalizability of study findings by dropping large numbers of cases.

The nearest neighbor and K-nearest neighbor algorithms are typically implemented without replacement, meaning that when control candidate i has been selected as a match for case member 1, he/she is no longer available as a match candidate for case member 2. In this arrangement, the order in which the matching is implemented across patients will affect the quality of the overall match. For example, if individuals are first ranked by age, a slightly different result will be obtained than if individuals are first ranked by decreasing propensity score.

The study team will select a specific propensity score matching method following a thorough inspection of the analytic dataset. If the sample sizes for cases and controls are large enough we will consider using nearest neighbor with caliper matching. If this is not the case or if this approach fails to find a match for a large number of empagliflozin add-on patients (>10% of the cases fail to match), we will loosen the caliper width to up to 0.6 (where bias reduction is still up to >90%). Alternatively, if we are unable to find a good match for over 10% of the cases even after loosening the caliper width to 0.6, we will consider using matching with replacement. If we are still unable to match an acceptable number of cases, we will implement inverse probability of treatment weighting (IPTW), which allows for complete inclusion of the cases.

Following the International Society for Pharmacoeconomics and Outcomes Research (ISPOR) best practices, [70] as a validation measure we will examine whether there are large differences in observed attributes (covariate values) of the empagliflozin add-on patients and the reweighted control group by assessing visual tools, such as density balance plots, and standardized mean differences. We will determine that the covariates are well-balanced if standardized mean differences do not exceed 10%. These analyses will serve as tools for assessing the quality of the matching procedure.

Step 2: Calculate descriptive statistics

We will then use our matched cohorts to calculate descriptive statistics of the baseline characteristics of our patient population (separately for the empagliflozin cohort, the sulfonylurea cohort, and the overall population). After calculation of standardized mean differences, chi-square tests will be used to assess statistically significant differences for categorical variables, and t-tests will be used to assess statistically significant differences for continuous variables.

Step 3: Construct statistical models of primary and secondary outcomes

Using observed safety and effectiveness events, we will calculate incidence rates and 95% confidence intervals for IPTW/PSM matched cohorts. We will estimate the hazard ratios and confidence intervals via Cox regression for primary outcome of interest, comparing empagliflozin vs. comparison group. We will also estimate differences in healthcare utilization using incident counts, by performing either Poisson or negative binomial regression, and differences in cost outcomes will be assessed by generalized linear regression using a Gamma family log link function.

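### The last step of the matching ladder weights all empagliflozin patients at the point where failed matching would indicate that propensity scores do not overlap

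*Protocol*

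**What the plan says.** Section 9.7.1, Step 1, sets a sequence for building the comparison cohort:

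1. Caliper matching: "If the sample sizes for cases and controls are large enough we will consider using nearest neighbor with caliper matching". The caliper given as usual practice is 0.2: "often caliper width equaling 0.2 of the standard deviation of the logit of propensity score is used".
2. If this fails for too many patients (">10% of the cases fail to match"), a wider caliper: "we will loosen the caliper width to up to 0.6 (where bias reduction is still up to >90"%).
3. If more than 10% are still unmatched, replacement: "even after loosening the caliper width to 0.6, we will consider using matching with replacement".
4. Last, if too few cases can still be matched, weighting: "we will implement inverse probability of treatment weighting (IPTW), which allows for complete inclusion of the cases". The stated merit is that all cases are kept.

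The balance check that follows uses density plots and a 10% limit on standardized mean differences (SMDs). It states no action if the limit is exceeded. Step 3 then fits the Cox model for the primary outcome, hospitalization for heart failure (HHF), in the resulting cohort. Section 9.5 assumes in its sample-size reasoning that IPTW balances the arms.

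Two other places describe the choice differently. The Abstract (Data analysis) uses IPTW when the matched sample is too small for a powered analysis. Section 9.1 names IPTW first and matching as the option if numbers permit.

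**The concern.** Matching without replacement can fail because cases compete for the same few controls. Matching with replacement removes that competition. A case that still has no partner within a wide caliper has no comparable control in the data. Inverse probability weighting needs comparable patients in both arms across the range of the propensity score (PS), and it cannot supply controls that are absent.

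The ladder therefore uses a method that depends on overlap after its own earlier steps have pointed to a lack of it. It also presents keeping the unsupported cases as the advantage, and no step restricts the analysis to the region of overlap. At stake is the primary HHF hazard ratio, which could rest on a handful of heavily weighted patients or include cases with no real comparator.

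**Working it through.** **Inputs from the protocol (section 9.5).** The rows with any metformin supply give:
- empagliflozin: 461 + 331 + 375 + 801 = 1,968
- comparator: 8,771 + 10,409 + 14,275 + 17,029 = 50,484
- ratio: 50,484 / 1,968 = 25.7 to 1
- share treated: 1,968 / 52,452 = 3.75%

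This takes the column headed as the metformin sample to be the comparator pool. The protocol notes that the final numbers will differ. The 10% trigger corresponds to about 197 of 1,968 cases.

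**The plan's own figure.** The Schoenfeld formula with HR 0.65, equal arms, two-sided 5% and 80% power gives (1.96 + 0.842)² / [(ln 0.65)² × 0.5 × 0.5] = 169.2 events, which agrees with the stated 169. It needs Z = 1.96; the printed 0.96 would give about 70.

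**The sample-size route to IPTW.** With 1,968 matched pairs, the mean event rate is (14.5 + 9.4) / 2 = 11.95 per 1,000 patient-years. Then 169 / 0.01195 ≈ 14,140 patient-years, and 14,140 / (2 × 1,968) ≈ 3.6 years per patient. Follow-up stops at a refill gap of more than 30 days, so the route in the Abstract and section 9.1 is plausible, and it need not involve non-overlap.

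**When the ladder in 9.7.1 reaches IPTW.** The overlap is not known from the protocol, so it was varied. A linear score was drawn from N(d, 1) in 1,968 cases and N(0, 1) in 50,484 controls, with logit PS = ln(1,968 / 50,484) + d·x − d²/2. Calipers are in SD of the logit. Effective sample size is (Σw)² / Σw². The table gives means of five replicates. The two match columns show the share of cases unmatched at the 0.6 caliper.

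| d | without replacement | with replacement | effective treated, ATE | effective controls, ATT |
|---|---|---|---|---|
| 1 | 0% | 0% | 772 | 18,369 |
| 2.5 | 25% | 1% | 42 | 232 |
| 3.5 | 62% | 9% | 10 | 34 |
| 4 | 75% | 20% | 12 | 21 |

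A hand check supports the replacement column. The 1-in-50,484 upper quantile of a standard normal is 4.11, so cases above about 4.11 + 0.6 = 4.71 have no partner. That is P(Z > 1.21) = 11% at d = 3.5 and P(Z > 0.71) = 24% at d = 4.

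At d = 2.5 the failure is competition for controls, and replacement solves it. More than 10% failing with replacement needs d of about 3.5 to 4.

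**What IPTW does at d = 3.5 to 4.**
- ATE weights: 20 treated patients carry about 82% of that arm's weight. The largest weights are about 28,500 to 40,000, and the residual SMD is 0.36 to 0.82.
- ATT weights: 20 controls carry 53% to 68% of the weight, and the residual SMD is 0.17 to 0.32.
- Overlap weights: about 420 to 690 effective treated patients and 760 to 1,370 effective controls.

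The residual SMDs vary between replicates, but these averages all exceed the protocol's limit of 0.10.

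**Variant: 10% to 30% of cases with no controls at all, good overlap elsewhere (d = 1).** ATT weights stay below 2, but 10% to 30% of the target population has no comparator. ATE weights on treated patients still reach about 430 to 660.

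**The case against.** **The trigger may not mean non-overlap.** The protocol does not say that the 0.6 caliper still applies with replacement, and without a caliper every case would match. What counts as an acceptable number matched is also undefined. This stands as an assumption. It is the natural reading, because otherwise the last step could never be reached.

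**IPTW is not reserved for this situation.** A reader might infer that the plan uses IPTW only when overlap has failed. The protocol as a whole does not support that: the Abstract and section 9.1 also lead to IPTW when the matched sample is too small. The point is confined to the ladder in 9.7.1.

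**The cost under ordinary overlap.** A reader might also infer that IPTW would be badly imprecise even with good overlap. With a logit-PS SD of 1.0 to 1.5, ATE weights would give a standard error of the log hazard ratio of about 0.37 to 0.63 at one year, against 0.24 to 0.25 with overlap weights. The protocol does not support using these figures here. In those scenarios only 0.07% to 1.1% of cases fail even at a 0.2 caliper without replacement, so the ladder stops at its first step. The weight type is also not stated. The balance paragraph speaks of reweighting the controls, which suggests ATT weights, and those give about 0.24 to 0.25 as well.

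**Safeguards and the SAP.** The SMD check and density plots would probably expose the problem, and truncation or trimming may be set out in an SAP that is not shown. But the protocol ties no action to a failed check, and it fixes the all-cases rule itself. Taking that phrase as a bar on common-support restriction is an interpretation; it may only contrast IPTW with dropping cases by caliper. Even so, no step of the ladder provides for restriction.

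**Conclusion.** The point holds conditionally. If the ladder in 9.7.1 runs to its last step, with the caliper kept under replacement and a pool near 26 to 1, the failure indicates non-overlap and IPTW on all cases does not repair it. In the assumed scenarios that trigger the step, one arm's effective sample falls to about 10 treated patients (ATE) or about 20 to 40 controls (ATT), against several hundred or more per arm with overlap weights. If some cases have no controls at all and ATT weights are used, the harm is comparison without support, not extreme weights.

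The actual overlap is unknown, the separations are assumptions, and the counts are preliminary. The documents do not show that this step will be reached. The change is still worth making before analysis, because the rule governs the primary estimate.

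**What to change.** In section 9.7.1:
- Before any IPTW, restrict both arms to the common propensity-score range, or replace the fallback with overlap weights (1 − PS for empagliflozin, PS for sulfonylurea). After range restriction, recheck the effective sample, because large weights can remain near the edge of the range.
- Report the number and characteristics of cases outside overlap.
- Remove complete inclusion of cases as the rationale for IPTW.
- Reconcile the IPTW triggers in the Abstract, section 9.1 and section 9.7.1.

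The cost is protocol and SAP wording and, for overlap weights, one changed weight formula. The scientific price is a narrower target population: the estimate applies only to patients who could plausibly have received either treatment, and the report must say so.

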Stable angina; n (%)			
Other chronic ischemic heart disease; n (%)			
Previous coronary revascularization; n (%)			
Ischemic or hemorrhagic stroke; n (%)			
Ischemic stroke; n (%)			
Transient ischemic attack; n (%)			
	1	1	

Hemorrhagic stroke and other cerebrovascular disease; n $\binom{6}{3}$		
Late effects of cerebrovascular disease or procedure; n		
(%)		
Heart failure; n (%)		
Peripheral arterial disease or surgery; n (%)		
Atrial fibrillation; n (%)		
Other cardiac dysrhythmia; n (%)		
Other cardiovascular disease; n (%)		
Hypertension; n (%)		
Hyperlipidemia ; n (%)		
Edema; n (%)		
Non-diabetic renal dysfunction; n (%)		
Acute kidney injury; n (%)		
Chronic kidney disease; n (%)		
Chronic kidney disease stage 1-2; n (%)		
Chronic kidney disease stage 3+ or dialysis; n (%)		
Hypertensive nephropathy; n (%)		
Miscellaneous renal insufficiency ; n (%)		
Kidney or bladder stones; n (%)		
Urinary tract infections; n (%)		
COPD; n (%)		
Asthma; n (%)		
Obstructive sleep apnea; n (%)		
Pneumonia; n (%)		
Liver disease; n (%)		
Osteoarthritis; n (%)		
Other arthritis, arthropathies and musculoskeletal pain; n (%)		
Dorsopathies; n (%)		
Fractures; n (%)		
Falls; n (%)		
Osteoporosis; n (%)		
Disorders of thyroid gland; n (%)		
Depression; n (%)		
Anxiety; n (%)		
Sleep disorders; n (%)		
Dementia; n (%)		
Delirium; n (%)		
Psychosis; n (%)		
Angiotensin converting enzyme inhibitors; n (%)		
Angiotensin II receptor blockers; n (%)		

Beta-blockers; n (%)		
Calcium-channel blockers; n (%)		
Thiazide diuretics; n (%)		
Loop diuretics; n (%)		
Other diuretics; n (%)		
Nitrates; n (%)		
Other hypertension drugs; n (%)		
Digoxin; n (%)		
Anti-arrhythmics; n (%)		
COPD or asthma medications; n (%)		
Statins; n (%)		
Other lipid-lowering drugs; n (%)		
Antiplatelet agents; n (%)		
Oral anticoagulants; n (%)		
Heparin and other low-molecular weight heparins; n (%)		
Nonsteroidal anti-inflammatory drugs; n (%)		
Oral corticosteroids; n (%)		
Bisphosphonates; n (%)		
Opioids; n (%)		
Antidepressants; n (%)		
Antipsychotics; n (%)		
Anticonvulsants; n (%)		
Benzodiazepines; n (%)		
Other anxiolytics or hypnotics; n (%)		
Dementia medications; n (%)		
Antiparkinsonian medications; n (%)		
Hospitalization within prior 30 days; n (%)		
Hospitalization during prior 31-365 days; n (%)		
No. hospitalizations; mean (sd)		
No. hospital days; mean (sd)		
No. emergency department visits; mean (sd)		
No. office visits; mean (sd)		

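### The matching ladder is steered by numbers of patients, not balance: failing the protocol's own 10% SMD limit has no stated consequence, so the rule can settle on an imbalanced cohort for the primary HHF hazard ratio

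*Protocol*

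**What the plan says.** Protocol section 9.7.1, Step 1, sets the order of methods.

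- **Entry:** "If the sample sizes for cases and controls are large enough we will consider using nearest neighbor with caliper matching".
- **First remedy:** if samples are too small, or if "this approach fails to find a match for a large number of empagliflozin add-on patients (>10% of the cases fail to match"), the caliper is relaxed to as much as 0.6. The text adds that bias reduction can still be above 90% at that width.
- **Second remedy:** matching with replacement is considered "if we are unable to find a good match for over 10% of the cases even after loosening the caliper width to 0.6".
- **Last rung:** IPTW, if the number of matched cases is still not acceptable.

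The abstract's data analysis row also chooses between matching and IPTW, on whether the matched sample leaves enough power.

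The balance check follows the ladder and is introduced as validation: "We will determine that the covariates are well-balanced if standardized mean differences do not exceed 10" (per cent). Its stated use is: "These analyses will serve as tools for assessing the quality of the matching procedure".

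Step 2 adds chi-square and t-tests on baseline variables, with no action attached. Step 3 estimates the hazard ratio "via Cox regression for primary outcome of interest, comparing empagliflozin vs. comparison group" and uses count and Gamma models for utilisation and cost. No adjustment covariates are named for any of them. Baseline heart failure is collected as one row of the covariate table in section 9.3 ("Heart failure; n").

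**The concern.** The protocol states both a selection rule and a standard of balance, but the rule never consults the standard. Where retention and balance conflict, retention wins: losing more than 10% of cases sets off a wider caliper, while an SMD above 10% sets off nothing. The first remedy also gives up closeness of match to keep cases. Section 9.7.1 itself describes calipers as a way to guarantee a minimum match quality and cites 0.2 SD of the logit of the propensity score as the usual width.

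This matters because balance on measured covariates is the study's main protection. Section 9.3 expects confounding by indication, and section 9.9 concedes that HbA1c, creatinine and socioeconomic status are unavailable. The primary outcome is hospitalisation for heart failure, so a leftover difference in heart failure history would act directly on the headline hazard ratio.

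**Working it through.** **Step 1. Every trigger in the document**

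| Decision | Stated trigger | Depends on SMD? |
|---|---|---|
| Matching or IPTW (abstract; 9.1) | Sample size or power after matching | No |
| Start with caliper matching (9.7.1) | Samples large enough | No |
| Relax caliper to at most 0.6 | Samples too small, or more than 10% of cases unmatched | No |
| Consider replacement | No good match for more than 10% of cases at 0.6 | No |
| Move to IPTW | Number of cases matched not acceptable | No |
| Any step after IPTW | None stated | No |
| Instrumental variable model (9.7.2) | Feasibility | No |

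No row depends on the 10% limit. A cohort with 92% of cases matched and an SMD of 15% on one covariate meets every condition for stopping on the first rung.

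**Step 2. What a failed check could do to the hazard ratio**

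The document gives no heart failure prevalence and no association between heart failure history and HHF, so both are assumed here. Let p0 be the prevalence in the arm with less heart failure, p1 the prevalence in the other arm, and R the hazard ratio of HHF for patients with heart failure history.

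- p1 solves SMD = (p1 − p0) / √{[p1(1 − p1) + p0(1 − p0)] / 2}
- Bias factor B = [1 + p1(R − 1)] / [1 + p0(R − 1)], a rare-event approximation

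With p0 = 0.20 and R = 5, the denominator of B is 1 + 0.20 × 4 = 1.80. The last two columns apply B to the design hazard ratio of 0.65 (section 9.5), as 0.65 / B and 0.65 × B.

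| SMD | p1 | B | True 0.65 reads, if heart failure is rarer on empagliflozin | True 0.65 reads, if it is commoner |
|---|---|---|---|---|
| 10% | 0.241 | 1.09 | 0.60 | 0.71 |
| 15% | 0.263 | 1.14 | 0.57 | 0.74 |
| 20% | 0.285 | 1.19 | 0.55 | 0.77 |

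Example at 15%: (1 + 0.263 × 4) / 1.80 = 2.052 / 1.80 = 1.14. A true hazard ratio of 1.00 would read 1 / 1.14 = 0.88 at SMD 15% and 1 / 1.19 = 0.84 at SMD 20%, if heart failure is rarer on empagliflozin.

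**Step 3. Range of the assumptions**

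Over p0 from 10% to 30% and R from 3 to 8, B − 1 runs from 5% to 13% at SMD 10%, from 8% to 20% at SMD 15%, and from 11% to 28% at SMD 20%.

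**The case against.** Several counter-arguments have force.

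- **A separate analysis plan could supply the missing step.** Section 6 schedules one, and model covariates and propensity score respecification are often left to it. This stands for the covariate list. A reader might infer that the outcome models are unadjusted, or that a failing cohort goes straight into the hazard ratio. The protocol is silent on both and does not say that imbalance is ignored. It does fix both the ladder and the limit, so the missing link between them is a fault of this text.
- **The share of cases matched is not the only trigger.** That is right: sample size and power count too. The method is also to be chosen after inspecting the data, and a match within a caliper reflects some closeness of score. None of these is a test of covariate balance.
- **There is another provision for residual confounding.** The instrumental variable analysis exists, so it would be wrong to say there is nothing further. It is exploratory, rests on feasibility and is not prompted by imbalance.
- **A single 10% limit is conventional.** Agreed. A reader might want a tighter limit for heart failure, or exact matching on it. Those are design preferences, and the document does not contradict itself by doing without them.
- **The size is hypothetical.** Also agreed. Heart failure is among the baseline covariates, so matching may well balance it; nothing in the document predicts an SMD of 15-20%. The arithmetic shows what an unanswered failure would cost, not that one will occur.

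**Conclusion.** The point holds as a defect in the selection rule. Section 9.7.1 chooses the method on quantity alone, relaxes match quality first, and attaches no consequence to failing its own balance limit, including under IPTW. The ladder can therefore settle on a cohort for the primary analysis that the protocol would itself call not well balanced.

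The possible size is a factor of 1.14-1.19 on the hazard ratio for an SMD of 15-20% on heart failure. This assumes 20% prevalence in one arm, a 5-fold HHF hazard, one binary confounder and no adjustment in the model. Other plausible inputs give 1.08-1.28 over the same SMDs. The document does not support the stronger conclusions that imbalance will occur or that the models are certain to be unadjusted.

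**What to change.** **In section 9.7.1, Step 1:**

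1. Accept a rung only if at least 90% of cases are retained and every covariate has an SMD at or below 10%.
2. If balance fails, respecify the propensity score (interactions, non-linear terms) without reference to outcomes and check again. If it still fails, move to the next rung.
3. At the last rung, IPTW, include in the outcome models any covariate whose weighted SMD still exceeds 10%. This applies only there, because the earlier rungs are not accepted with such an imbalance.

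**In section 9.7.1, Step 3:** state that the Cox model for HHF also adjusts for baseline heart failure, which is already collected.

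The abstract's choice between matching and IPTW should be worded to agree.

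**Cost:** a few sentences and a little programming, with no new data. The hazard ratio becomes conditional on heart failure history and should be labelled so. On the dates in section 6, the analysis plan is finalised (06/07/2021) before the analytic dataset is built (07/02/2021), so the rule can be fixed in advance.
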